5.2.3 Sensitivity Analysis

Pattern Mixture Analysis

A sensitivity analysis will be performed using a pattern mixture model with multiple imputation for missing data under the missing not at random (MNAR) assumption using the same approach as described for the primary analysis in Section 5.2.1. See Appendix 12.3 for further details.

Modified Multiple Imputation Analysis

The second sensitivity analysis may be carried out imputing C3G Histological Index of Disease Activity data for subjects who had clinical significant increase or new introduction of treatments

for C3G including MMF and/or prednisone after screening biopsy and prior to week 26 renal biopsy; should any of these changes invalidate histological activity scores at week 26. Identification of these medications will be performed and impacted subjects will be identified prior to Week 26 Primary Endpoint data freeze. Similar methodology as described for the primary analysis (ANCOVA) will be carried out. The same multiple imputation as specified for the primary analysis (Section 5.2.1) may be performed imputing C3G Histological Index of Disease Activity component scores and Disease Chronicity component scores after the initiation of the restricted medication. The imputed values will be used to calculate the C3G Histological Index of these variables. Identification of these medications will be performed and impacted subjects will be discussed and finalized prior to database lock.

Modified Multiple Imputation method may be explored for the percent change and change from Week 26 to Week 52 during the avacopan treatment period.

Additional Modified Multiple Imputation Analysis may be conducted to explore other aspects of changes of treatments for C3G, such as clinical significant dose decreases of immunosuppressants, glucocorticoids, or ACE inhibitors/ARBs in Period A.

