Study medication must be permanently discontinued ([FDA Guidance 2009](#)) if any of the following markers of hepatic injury and/or impaired liver synthetic function are observed, and cannot be attributed to a reversible etiology unrelated to study medication (e.g., cholelithiasis):

- ALT or AST $>8x$ ULN
- ALT or AST $>5x$ ULN for more than 2 weeks
- ALT or AST $>3x$ ULN and (Total Bilirubin $>2x$ ULN or INR >1.5)
- ALT or AST $>3x$ ULN with the appearance of fatigue, nausea, vomiting, right upper quadrant pain or tenderness, fever, rash, and/or eosinophilia ($>5\%$)

If a patient develops Grade 3 or greater leukopenia (WBC count $<2 \times 10^9/L$) or neutropenia ($<1 \times 10^9/L$), or Grade 4 lymphopenia ($<0.2 \times 10^9/L$), then study drug (avacopan or placebo) must be paused in this patient. In addition, if a patient develops Grade 2 leukopenia (WBC count $<3 \times 10^9/L$, but $\geq 2 \times 10^9/L$), the patient must be followed closely for infection and for further significant reduction (reduction by an additional $0.5 \times 10^9/L$ or more, or to $<2 \times 10^9/L$) in WBC count; if either occurs, then study drug must be paused in this patient. Study drug may be resumed only if the abnormal value returns to normal and the Investigator deems resumption to be appropriate.

If a patient develops Grade 3 or worse CPK increase (>5 times the upper limit of normal), dosing with study drug must be paused in this patient. Study drug may be resumed only if the CPK returns to normal levels.

Patients who experience deteriorating renal function based on an increase in serum creatinine of at least 50% (confirmed by a repeat measurement after at least 2 weeks) which is otherwise not explained (e.g., dehydration, new medication), or an increase in proteinuria of >3 g/g creatinine (confirmed by a repeat measurement after at least 2 weeks) from Screening or baseline during the 52-week treatment period, will exit the treatment phase of the study and be treated at the discretion of their physician. The increase of serum creatinine or proteinuria will be calculated from the higher value that is measured either at Screening or baseline. They will remain in the study for follow up and complete the remaining study visits and procedures. If a patient refuses further study participation, the Early Termination visit procedures will be performed, if possible. These patients will be considered treatment failures.

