Data from patients who are treatment failures, i.e., requiring treatment rescue measures such as high dose glucocorticoids during the treatment period, will be excluded from efficacy analysis after the point of rescue treatment.

Since the placebo group will receive avacopan during the second 26 weeks of the study, the change from Week 26 to Week 52 in the C3G Histologic Index for activity in the placebo control group will be compared to the change from baseline to Week 26 in this group. This analysis will be done by the paired t-test. Point estimates and corresponding 95% confidence intervals will be estimated for the difference between the second 26 weeks (avacopan treatment) and the first 26 weeks (placebo treatment).

The change from baseline to Week 52 in the C3G Histologic Index in the avacopan group will also be compared to the change from baseline to Week 26 in placebo control group using similar methodology as described for the primary efficacy endpoint.

Continuous variables, including eGFR, UPCR, urinary MCP-1:creatinine ratio, EQ-5D-5L, and SF-36 v2 will be analyzed using a mixed effects model for repeated measures (MMRM) with treatment group, visit, and treatment-by-visit interaction as factors, and baseline as covariate. Patients will be considered as repeated measure units over visits. The interaction term may be dropped if it is not significant at $\alpha = 0.25$ level. Point estimates and corresponding 95% confidence intervals will be estimated for the difference between the avacopan group and the control group at Week 26 using simple contrast from the model.

Similar to the primary endpoint, the second 26 weeks will be compared to the first 26 weeks for the placebo group. Changes in the efficacy parameters across 52 weeks will also be assessed.

Change and percent change in the efficacy parameters during the 8-week follow-up period will also be assessed to determine the off-treatment effect.

Change from baseline in individual components of the C3G Histologic Index activity and chronicity indices as well as glomerular leukocytes and leukocyte subsets based on immunohistochemistry will be summarized and, where appropriate, analyzed using similar methodologies as describe above.

The secondary endpoint of the proportion of patients who have a histologic response will be analyzed by the CMH chi-square test. Data from patients who are treatment failures, i.e., require rescue medication, will be summarized.

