8.8. Sample Size Justification

A sample size of 22 patients per treatment group (avacopan and placebo, respectively) in each of the C5b-9 level strata is based on the between-treatment difference of -35% in the C3G Histologic Index for activity at Week 26, standard deviation (SD) 34%, power 90%, and 2-sided $\alpha = 0.05$.

The sample size of 22 per group also provides approximately 90% power to detect a delta of -35% in the C3G Histologic Index for activity between the percent change from baseline in the first 26 weeks and in the second 26 weeks, assuming an SD of 34% for each change.

The mean treatment effect size of 35% is considered reasonable based of the following:

- Of the 5 patients with histologic data in the study by [Herlitz et al., 2012](#) with eculizumab, an anti-C5 antibody, 2 patients had a 67% decrease (improvement) in histologic score, 1 had a 43% decrease, and 2 had no change from baseline; the mean decrease for the 5 patients was 35%;
- An improvement in the histologic score of at least 35% is considered clinically meaningful by clinical and histology experts;
- The SD for the percent change from baseline in C3G Histologic Index of activity was 34% in the Herlitz study; a change of 35% of greater will be above the observed variance for this parameter.

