3 STATISTICAL METHODOLOGY

3.1 General Considerations

For efficacy analysis, to control for the Type I error rate, a gate-keeping procedure will be applied for the analysis of the primary efficacy endpoint (percent change in C3G Histologic Index for disease activity). The primary endpoint will be tested in the elevated C5b-9 stratum first with a two-sided $\alpha = 0.05$. If this test reaches statistical significance, then the primary endpoint will be tested in the combined C5b-9 strata (including both elevated and non-elevated C5b-9 strata) with a two-sided $\alpha = 0.05$. If the test in the elevated stratum fails to reach statistical significance, then the test in the combined C5b-9 strata will only be performed as an exploratory analysis. The statistical analysis for the secondary endpoint (C3G Histologic Index for disease chronicity) will be tested at a 0.05 α -level only if the primary endpoint in the same stratum reaches statistical significance.

Data will be summarized descriptively by treatment group as well as separately for the elevated C5b-9 stratum and combined strata. For continuous variables, numbers, means, medians, ranges, standard deviations, and standard error of means will be calculated. Geometric means will be calculated for UACR and urinary MCP-1:creatinine ratio, and other data that are not normally distributed. Frequency counts and percentages will be presented for categorical variables. Listings of raw and derived data will be included as part of an appendix to the CSR.

In analysis tables and listings, the two treatment groups will be referred to as

- 'Placebo', referenced in the protocol as Group A (placebo)
- 'Avacopan', referenced in the protocol as Group B (avacopan)

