5.3.4 Proportion of subjects who have a histological response

Histological response is defined as a decrease (improvement) in the C3G Histological Index for disease activity of at least 35% from baseline to Week 26. See Section 2.3.4 for further details.

5.3.4.1 Primary Analysis

For the responder analysis, data of the patients who had clinical significant increase or new introduction of treatments for C3G including MMF and/or prednisone after screening biopsy and prior to week 26 renal biopsy and were identified in the Modified Multiple Imputation Analysis will be imputed as non-responder after the initiation of rescue concomitant medication. The number and proportion of subjects who have a histological response will be presented for each treatment group. Differences between avacopan and placebo will be analyzed using the Cochran-Mantel-Haenszel (CMH) chi-square test.

The code used to generate the analysis will be similar to the following:

Additionally, the number and percent of subjects whose histological activity scores at week 26 had been invalidated because of a clinical significant dose increase or new introduction of medication to treat C3G including MMF and/or prednisone after screening biopsy and prior to week 26 renal biopsy will be summarized. For the responder analysis, data will be imputed as non-responder after the initiation of rescue concomitant medication. Concomitant medications
and other data such as adverse events will reviewed prior to database lock to determine if reason for medication use is considered to be for rescue.

Modified Multiple Imputation method may be explored for the proportion of subjects who have a histological response.

5.3.5 Change from baseline in urinary MCP-1:creatinine ratio during the 26 Week placebocontrolled treatment period

The same analysis as described for UPCR will be carried out for urinary MCP-1:creatinine ratio including primary and secondary analyses. Urinary MCP-1:creatinine ratio is computed at Baseline, Weeks 1, 2, 4, 12, 20, 26 during the 26 week double-blind treatment period and Weeks 28, 32, 38, 52 and 60 during the avacopan treatment and follow-up periods.

5.3.6 SF-36 v2 and EQ-5D-5L VAS and Index - Change from Baseline during the 26 Week placebo-controlled treatment period

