10 CHANGES FROM PROTOCOL-SPECIFIED STATISTICAL ANALYSES

- The protocol specified 3 analysis populations for the study including the primary elevated C5b-9 population, the non-elevated C5b-9 population and the combined population. Due to the small sample size in the non-elevated C5b-9 stratum, the primary elevated C5b-9 population will remain as the primary population and the two strata combined (including both elevated and non-elevated C5b-9) will be considered the secondary population for analysis. Data from the non-elevated C5b-9 stratum will only be summarized.
- ITT population definition change to exclude subjects who had baseline C3G Histologic Index of activity score of 0.
- Secondary efficacy endpoint order rearranged.

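### The SAP sets no rule for data after protocol-defined treatment failure in its main models, its optional rescue imputation borrows from the same arm, and renal-deterioration failures can still count as responders

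*SAP*

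**What the plan says.** **Protocol.** There are two routes to treatment failure.

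- Sections 3.4 and 5.9: adding C3G treatment, or increasing concomitant immunosuppressive or glucocorticoid treatment, with RAAS inhibitors excepted.
- Section 4.4: a confirmed and otherwise unexplained creatinine rise of at least 50%, or a confirmed proteinuria rise above 3 g/g. These patients leave study drug but complete the remaining visits and procedures, so a Week 26 biopsy can exist. "These patients will be considered treatment failures".

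Under Section 8.7.5, data from failures who need rescue measures "will be excluded from efficacy analysis after the point of rescue treatment". Section 8.7.6 fills missing histology by LOCF, which may mean the baseline value.

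**SAP.** Section 1 says that its methods supersede the protocol's.

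- 5.2.1 imputes missing data only, under MAR. It has no rule for data after rescue.
- 5.2.3 offers a rescue analysis: "The same multiple imputation as specified for the primary analysis (Section 5.2.1) may be performed imputing C3G Histological Index" component scores. It is optional and depends on a judgement that the medication change invalidates the Week 26 score. Appendix 12.3 runs the primary imputation separately by arm. The same appendix codes a placebo-reference MNAR step, which 5.2.3 assigns to missing data.
- 3.2.4 and 5.2.6 require a per-protocol analysis. Grounds for exclusion include new C3G treatments and clinically significant MMF or prednisone increases.
- 5.3.1.1 is an MMRM for UPCR with no rescue rule. The sensitivity analysis in 5.3.1.4 covers ACE inhibitor/ARB changes. 5.3.2 carries the UPCR primary and secondary analyses over to eGFR and adds nothing on rescue.
- 5.3.4.1 says that patients with a clinically significant increase in, or new, C3G treatment "will be imputed as non-responder after the initiation of rescue concomitant medication".
- Section 10 lists three changes from the protocol: the C5b-9 analysis populations, "ITT population definition change to exclude subjects who had baseline C3G Histologic Index of activity score of 0", and the order of the secondary endpoints.

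**The concern.** One clinical event is handled in several ways. A patient rescued with MMF or prednisone is excluded after rescue under the protocol. In the SAP the same patient is kept as observed in the primary analysis (by silence), possibly imputed from the same arm in 5.2.3, considered for removal in the per-protocol set, and scored a non-responder in 5.3.4.1. A patient taken off drug for renal deterioration, with no C3G treatment change identified, is a failure in the protocol and has no specific rule anywhere in the SAP's efficacy analyses.

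Two things are at stake. First, neither activity-index analysis that deals with rescue lets a failure count against the arm in which it occurred: one removes the patient, the other gives the patient a value typical of those who did not fail. Second, a patient whose kidney function worsened enough to stop study drug can be reported as a histologic responder. For UPCR, the medication class given a sensitivity analysis is within the one the protocol exempts from failure (RAAS inhibitors), while immunosuppressant and glucocorticoid rescue, which does define failure, has none.

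**Working it through.** **1. Reproduce the planning figure.** Protocol 8.8: the sample size "is based on the between-treatment difference of -35% in the C3G Histologic Index for activity at Week 26", with SD 34, 90% power, two-sided 0.05 and 22 per arm per stratum.

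- Normal approximation: n = 2(1.960 + 1.282)² × (34/35)² = 19.8, so 20 per arm.
- Exact t-test: 21 per arm gives 90.2% and 22 gives 91.6%.
- The five cited eculizumab patients (−67, −67, −43, 0, 0) have mean −35.4 and SD 33.8.

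The plan's figures hold and serve as inputs below.

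**2. Assumptions.** The documents give no failure rate, so the counts are illustrative. Non-failures average −35% on avacopan and 0% on placebo. A failure left unrescued averages 0%. There are 22 per arm. Let kA and kP be the failures on avacopan and placebo.

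**3. Within-arm imputation (SAP 5.2.3).** Failures receive values from a model fitted to patients in the same arm who did not fail, so the avacopan mean stays at −35 whatever kA is. Counting failures at 0% gives −35(22 − kA)/22. The overstatement is 35kA/22. In a placebo arm with no mean change, the same step adds nothing on average.

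| kA of 22 | Difference, within-arm MAR | Difference, failures at 0% or from placebo | Overstatement |
|---|---|---|---|
| 1 | −35.0 | −33.4 | 1.6 |
| 2 | −35.0 | −31.8 | 3.2 |
| 3 | −35.0 | −30.2 | 4.8 |
| 4 | −35.0 | −28.6 | 6.4 |

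The third column is also what the protocol's exclusion plus LOCF to baseline would give. At 22 per arm with SD held at 34, normal-approximation power is 92.7% for −35.0, 87.4% for −31.8 and 79.8% for −28.6. Removing failures, as the per-protocol analysis does, also leaves the expected avacopan mean at −35.

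**4. Observed post-rescue data (SAP primary, read literally).** Assume rescue itself produces −35% in either arm. The avacopan mean stays at −35 and the placebo mean becomes −35kP/22, so the difference is −35 + 35kP/22: −31.8 with two placebo rescues and −28.6 with four. Relative to counting failures at 0%, the gap is 35(kP − kA)/22. Benefit is overstated if avacopan has more rescues, understated if placebo has more, and unaffected if the counts are equal.

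**5. Responders.** One patient is 1/22 = 4.5 points of an arm's response rate. That is the shift when an uncovered renal-deterioration failure is in fact scored as a responder. If such patients average 0% with SD 34, the chance of a fall of at least 35% is Φ(−35/34) = 0.15, so the expected shift per uncovered patient is 0.15 × 4.5 = 0.7 points. The normal model is rough for a 0–21 integer score.

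**The case against.** Several points on the other side stand.

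- **The per-protocol analysis is required and does address rescue.** One might infer that the optional imputation is the SAP's only activity-index analysis of rescue; it is not. The compliance criterion (below 75%) could also catch a renal exit before about Day 137 (0.75 × 182 = 136.5) if the denominator is the full period. But the criteria are for consideration, and removal is not the same as counting a failure.
- **Medication-rescued patients are already non-responders.** A reader might infer that the SAP ignores failures altogether; 5.3.4.1 shows otherwise. Its wording includes MMF and prednisone without being limited to them, so the gap is confined mainly to renal-deterioration failures with no C3G treatment change identified.
- **The protocol does not exclude renal exits as such.** Section 8.7.5 ties exclusion to the point of rescue treatment, and the protocol's own responder endpoint has no non-responder rule. Scoring renal exits as non-responders is therefore an improvement consistent with Section 4.4, not the restoration of a dropped rule.
- **Keeping observed data is a defensible treatment-policy choice.** Protocol 4.4 asks for continued efficacy follow-up after drug discontinuation or medication changes, and the SAP may supersede the protocol. What remains is that the choice is neither stated nor listed, so a reader could equally argue that the protocol exclusion still applies.
- **Imputation conditions on baseline, disease type and transplant status.** This softens the borrowing but does not bring failure into the model.

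**Conclusion.** The point holds as a set of gaps that should be closed; it does not show that the primary result is biased towards avacopan. The stronger inference, that keeping post-rescue biopsies inflates the treatment effect, is not supported: step 4 shows that the direction depends on which arm has more rescues, and the documents do not say.

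What is established from the text: the protocol's post-rescue exclusion has no counterpart in the SAP and its absence is not listed in Section 10; the rescue imputation is optional and within-arm; UPCR and eGFR have no analysis for immunosuppressant or glucocorticoid rescue; and renal-deterioration failures can be scored as responders.

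The size, 1.6 to 6.4 points for one to four avacopan failures, applies to the optional sensitivity analysis only. It rests on the planned −35% effect and on failures truly not improving. The 4.5-point figure is per patient actually misclassified. Confidence is medium, because the failure counts are unknown.

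**What to change.** (a) **SAP 5.3.4.1:** keep the medication rule, including its start at the screening biopsy, and add that patients who meet the protocol's renal-deterioration failure definition before the Week 26 biopsy are non-responders.

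(b) **SAP 5.2.3:** make the rescue sensitivity analysis required and have it cover both failure routes. Set post-failure lesion scores to missing and impute them with the placebo-reference MNAR step in Appendix 12.3, alongside or instead of within-arm MAR.

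(c) **SAP 5.3.1.4 and 5.3.2:** add a sensitivity analysis of UPCR and eGFR for immunosuppressant or glucocorticoid rescue.

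(d) **SAP Section 10:** state that the primary analysis retains post-rescue data, contrary to protocol 8.7.5, and tabulate protocol-defined failures by arm and route. The SAP already summarises drug discontinuations, non-study C3G treatments and invalidated Week 26 scores, so only the combined table is new.

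The cost is SAP wording, reuse of existing code and one table, all settled before unblinding. No clinical rule changes. The downside is that the sensitivity and responder results may look less favourable to avacopan.

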5.2.4 Completer Analysis

A completer analysis will also be carried out requiring subjects in ITT to have valid C3G Histologic Index for disease activity scores at Baseline and Week 26. The primary analysis is based on percent change from baseline to Week 26 during the double-blind treatment period and will be analyzed using the ANCOVA analysis methods described above. The primary analysis will be based on the in the elevated C5b-9 stratum (>244 ng/ml). The same analysis will also be carried out for the combined C5b-9 strata (subjects with elevated C5b-9 blood levels and non-elevated C5b-9 blood levels). This analysis will be repeated for the change from baseline also.

5.2.5 Individual Components of C3G Histological Index Activity

Change from baseline in individual components of the C3G Histological Index Activities indices will also be summarized over time based on actual and imputed data.

5.2.6 Per-Protocol Analyses

The same analyses as described for the Primary Analysis will also be conducted in the Per-Protocol population.

Additional per-protocol analysis may be conducted to explore other aspects of changes of treatments for C3G, such as clinical significant dose decreases of immunosuppressants, glucocorticoids, or ACE inhibitors/ARBs in Period A

